
3 will receive TAK-071 placebo+donepezil placebo, 3 subjects will receive TAK-071 placebo+donepezil, and 6 subjects will receive TAK-071+donepezil).

In Cohorts 13 to 15, placebo treatments will be assigned in a 5:1 ratio (within each cohort of 6 subjects, 5 will receive active treatment and 1 will receive placebo. In Cohort 16, subjects will be assigned to 1 of 2 possible treatment sequences (AB or BA), with Treatment A being TAK-071 and Treatment B being matching placebo. In Cohort 17, subjects will be assigned to 1 of 3 possible treatments as Regimen Sequences ABC, BCA, and CAB, where, Regimen A=Fasted State and Capsule Formulation (10 mg in DIC formulation), Regimen B=Fasted State and Tablet Formulation (10 mg tablet formulation), and Regimen C=Fed State and Tablet Formulation (10 mg tablet formulation).

The safety of TAK-071 alone or in combination with donepezil or with/without food will be assessed through adverse events (AEs), clinical laboratory results, physical examination findings, electrocardiogram (ECG) findings, bowel function, vital signs, and suicidal assessments. Continuous 12-lead Holter ECG monitoring will also be performed on selected study cohorts.

The safety and tolerability of donepezil alone will be evaluated during the donepezil dosing phase (before TAK-071 is given in Cohorts 10 to 12) during the 3-week pretreatment period, and the safety and tolerability of donepezil in combination with TAK-071 (Cohorts 20 to 22) will be evaluated by assessing AEs, clinical laboratory results, physical examination findings, ECG findings, bowel function, and vital signs.

In addition to safety monitoring, TAK-071 plasma and urine PK profiles will be generated and PK parameters derived. It is planned that cerebrospinal fluid (CSF) samples for PK analysis will be obtained in Cohort 3 (following a single dose) and Cohort 9 (at steady-state). Pharmacodynamic measures will include the determination of pupil size and quantitative electroencephalography (EEG).

Approximately 186 subjects are expected to be randomized in this study.

End of study is defined as the date of last visit of the last subject for last clinical assessment.

Primary Objectives:

- To characterize the safety, tolerability, and plasma PK profile of TAK-071 when administered as single and multiple QD oral doses at escalating dose levels in healthy subjects (non-Japanese).

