4.4.5 Relative BA and FE Cohort (Cohort 17)

Cohort 17 will be administered in 3 single-dose regimens in a 3-way crossover design to 12 male and female subjects using 10 mg oral dose treatments. Subjects will receive a TAK-071 10 mg single oral regimen on Day 1 of each period. TAK-071 tablet or DIC will be administered with 240 mL of water.

Regimen A – Fasted State and Capsule Formulation (10 mg in DIC formulation)

Subjects will be fasted overnight for at least 8 hours. Treatment will be administered orally with 240 mL of water. No food should be allowed for at least 4 hours postdose. Water can be allowed after 2 hours postdose.

Regimen B – Fasted State and Tablet Formulation (10 mg [2× 5 mg] tablet formulation)

Subjects will be fasted overnight for at least 8 hours. Treatment will be administered orally with 240 mL of water. No food should be allowed for at least 4 hours postdose. Water can be allowed as desired after 2 hours postdose.

Regimen C – Fed State and Tablet Formulation (10 mg [2× 5 mg] tablet formulation)

Subjects will be fasted overnight for at least 8 hours. After this time, subjects should start the standard high fat meal (~50% fats) 30 minutes prior to administration of the drug product. Study subjects should eat this meal in 25 minutes or less. Drug product should be dosed 30 minutes after the start of the meal with 240 mL of water. No food should be allowed for at least 4 hours postdose. Water can be allowed as desired after 2 hours postdose.

Four subjects will be randomly assigned to 1 of 3 sequence groups and receive the regimens in the order shown in [Table 4.b](#).

Table 4.b Sequence Groups and Regimen Assignment for Cohort 17

Sequence Group	Number of Subjects	Period 1 Day 1	Period 2 Day 1	Period 3 Day 1
1	4	A	B	C
2	4	B	C	A
3	4	C	A	B

Regimen A: Fasted State and Capsule Formulation (10 mg in DIC formulation).

Regimen B: Fasted State and Tablet Formulation (10 mg tablet formulation).

Regimen C: Fed State and Tablet Formulation (10 mg tablet formulation).

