7.12 Safety Analysis

Within each part (SRD cohorts, MRD cohorts, Cohort 16, and Cohort 17), for the non-Japanese and Japanese SRD and MRD cohorts separately, all safety summary tables will be presented by the pooled placebo group, each TAK-071 dose level, TAK-071 overall, and overall total within each part (SRD cohorts, non-Japanese MRD cohorts, Japanese MRD cohorts, Cohort 16, and Cohort 17) in the Safety Set. Safety data collected after administration of study drug under fed conditions will be summarized separately from data collected during administration of the same dose level under fasted conditions.

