7.12.1 Adverse Events

A PTE will be defined as any untoward medical occurrence in a clinical investigation subject who has signed informed consent to participate in a study but prior to study drug (TAK-071 or placebo) administration or increase in dose/start of donepezil prior to TAK-071 dose. A TEAE will be defined as an AE or a serious AE (SAE) that occurs or gets worse after receiving the first dose of study drug and within 30 days (onset date – last date of dose + 1 ≤ 30) after the last dose of study drug. A TEAE may also be a pretreatment AE or a concurrent medical condition diagnosed prior to the date of first dose of study drug that increases in severity after the start of dosing. AE data with onset occurring more than 30 days after last dose of study drug (AE start date – last dose date > 30) will be listed, but not included in the summary tables.

AE verbatim reported terms will be coded by system organ class, high-level term and preferred term using MedDRA, version to be delineated in the CSR.

TEAE summary tables will include numbers and percentages of subjects experiencing at least one AE by system organ class (SOC) and preferred term (PT) and will be tabulated for SRD

cohorts, non-Japanese MRD cohorts, Japanese MRD cohorts, Cohort 16, and Cohort 17. TEAEs will be summarized according to the treatment most recently received prior to the onset of the event. The TEAE summaries for SRD cohorts, non-Japanese MRD cohorts, Japanese MRD cohorts will also include a treatment group for TAK-071 overall, including all TEAEs summarized for any dose level of TAK-071.

The following is a list of AE summary tables to be generated:

- Overview of TEAEs.
- TEAEs by SOC and PT at subject and event level.
- Subject Mappings for TEAEs.
- TEAEs by PT.
- Most Frequent TEAEs by PT.
- Most Frequent Non-Serious TEAEs by PT.
- Relationship of TEAEs to Study Drug by SOC and PT.
- Drug-Related TEAEs by SOC and PT.
- Intensity of TEAEs by SOC and PT.
- Intensity of Drug-Related TEAEs by SOC and PT.
- Pretreatment Events by SOC and PT.

A subject with 2 or more different AEs within the same level of the MedDRA term and TAK-071 dose level and pooled placebo will be counted only once in that level using the most extreme incident for the intensity tables, and related events to study drug for the causality tables.

Most frequent TEAEs are defined as the AEs occurring in at least 2 subjects in any treatment (ie, pooled placebo or individual dose level).

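### Read literally, the SAP's safety columns put both fasted regimens of Cohort 17 (capsule and tablet) together, so fasted at-least-once percentages cover two periods per subject and fed ones cover one

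*SAP*

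**What the plan says.** SAP 7.12, which names Cohort 17 among the parts covered, states that "all safety summary tables will be presented by the pooled placebo group, each TAK-071 dose level, TAK-071 overall, and overall total within each part". The only further division is by food: data after fed dosing "will be summarized separately from data collected during administration of the same dose level under fasted conditions".

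SAP 7.12.1 says that "TEAE summary tables will include numbers and percentages of subjects experiencing at least one AE" and that "TEAEs will be summarized according to the treatment most recently received prior to the onset of the event". Its definition of the most frequent events requires at least 2 subjects "in any treatment (ie, pooled placebo or individual dose level"). Its counting rule is that a subject with several events within the same MedDRA term and "TAK-071 dose level and pooled placebo will be counted only once in that level". SAP 7.12.2 to 7.12.4 repeat the dose-level columns for laboratory, vital-sign and ECG data, and report the percentage of subjects with at least one postdose MAV.

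SAP 4.4.5 defines the regimens: A is the 10 mg capsule fasted, C is the 10 mg tablet fed, and the middle one is "Regimen B: Fasted State and Tablet Formulation (10 mg tablet formulation"). Twelve subjects, four per sequence, take all three.

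On pharmacokinetics the SAP does name regimen. Section 7.10.1 lists it as a grouping for concentrations, and 7.10.2 summarizes the Cohort 17 parameters by it. On safety, Protocol 13.1.5 plans something else for the crossover cohorts: summaries by treatment sequence and in total, with no fed or fasted column.

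**The concern.** The primary safety endpoints (SAP 5.1) are percentages of subjects with an event at least once. Such a percentage rises with the number of periods over which a subject is watched. If one column covers two dosing periods per subject and its neighbour covers one, the two are not comparable even when nothing differs between regimens.

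A second problem is confounding. Fed (tablet only) against fasted (capsule and tablet) is not a clean food contrast, and the fasted tablet, which is the natural reference for both food and formulation, has no column of its own. Protocol 2.0 says "The safety of TAK-071 alone or in combination with donepezil or with/without food will be assessed", so a reader of the report will look for a fed and fasted comparison.

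**Working it through.** The documents give no computed figure on this point, so there is none to reproduce.

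**Inputs from the documents**
- Subjects: 3 sequences × 4 = 12 (SAP 4.4.5 and 6.0).
- Sequences ABC, BCA, CAB, all regimens 10 mg (SAP 4.4.5).
- Periods 1 and 2 last 21 days from dosing; Period 3 is followed to Day 12 (SAP Figure 4.g).

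**Assumptions**
- Every subject completes all three periods.
- The per-period risk p is the same in A, B and C. The documents give no rate, so a range is shown.
- Within-subject correlation ρ between periods is 0, 0.3 or 0.5.

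**Step 1: observation time.** Each regimen appears once in each period position, with four subjects each time: 4 × (21 + 21 + 12) = 216 subject-days. Fasted (A and B) has 432 and fed (C) has 216, which is exactly 2:1.

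**Step 2: expected percentage with at least one event.** Fed: p. Fasted, counting a subject once over two periods: p + (1 − ρ)p(1 − p). With ρ = 0 this equals 1 − (1 − p)², and the ratio to fed is 2 − p.

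| p (fed) | Fasted, ρ = 0 | Fasted, ρ = 0.3 | Fasted, ρ = 0.5 |
|---|---|---|---|
| 10% | 19% | 16% | 14.5% |
| 20% | 36% | 31% | 28% |
| 30% | 51% | 45% | 40.5% |

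For p = 20%: ρ = 0 gives 0.20 + 0.16 = 0.36; ρ = 0.3 gives 0.20 + 0.7 × 0.16 = 0.312; ρ = 0.5 gives 0.20 + 0.5 × 0.16 = 0.28. The gap closes fully only at ρ = 1. In subjects out of 12, with independent periods, this is 12 × 0.20 = 2.4 fed against 12 × 0.36 = 4.3 fasted.

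**Step 3: the rule for most frequent events.** For one preferred term with per-period risk r, the chance of at least 2 of 12 subjects is 1 − (1 − r)¹² − 12r(1 − r)¹¹. With r = 0.10 (fed) this is 34%. With the two-period value 0.19 (fasted, independent periods) it is 70%.

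**Step 4: how often the observed counts would mislead.** This was simulated with equal risk, independent periods and 12 subjects. The fasted count exceeds the fed count in 63% of trials at p = 10% (the reverse in 17%) and in 75% at p = 20% (the reverse in 13%). It is a tendency, not a certainty.

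**Step 5: after the change.** With one column per regimen, each column has 12 subjects and one period, so each expects p and the ratio under equal risk is 1.

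**The case against.** The strongest reply is that the SAP never says A and B are combined. It attributes events to the treatment most recently received, SAP 4.4.1 describes the Cohort 17 treatments in terms of the regimen sequences, and the PK summaries go by regimen. A programmer could therefore produce three columns. The gloss of treatment as placebo or dose level sits in the definition of most frequent events and is generic dose-escalation wording; Cohort 17 is open-label and has no placebo. This stands in part: the pooling follows from the named columns and is not an explicit instruction. But no safety section names regimen or formulation, the PK sections do, and the counting rule works within dose level. The text as written leads to two columns.

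Three stronger readings are tempting, and the documents do not support them.
- A reader might infer that the tablet's safety cannot be seen in any table. The fed column is Regimen C alone, so fed-tablet safety is visible. What is missing is the fasted tablet and the capsule–tablet contrast. Event listings, dosing times and subject mappings would let a reader trace events among 12 subjects.
- A reader might infer that laboratory, vital-sign and ECG averages are biased in the same way. They are not: SAP 7.1.3 sets baseline per period for Cohort 17, and a second record per subject does not inflate a mean or mean change.
- A reader might infer that fasted dosing will look less safe. Step 4 shows that this is only the likelier outcome, under assumed rates.

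It is also fair to say that little hangs on the comparison. The Cohort 17 objectives concern PK. The food phrase in Protocol 2.0 is absent from the matching sentences in Protocol 6.1 and SAP 4.4.1. SAP 7.12.2 and 7.12.3 rule out statistical tests, and no formal fed versus fasted safety comparison is specified. Under Protocol 13.1.5 the distortion would not arise, because there would be no food column; nor would there be any food or formulation comparison.

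**Conclusion.** Wrong as written, with low severity. Followed literally, SAP 7.12 and 7.12.1 set two fasted periods per subject against one fed period. Under equal true risk this tends to raise the fasted TEAE and MAV percentages, by a factor of 2 − p when periods are independent (1.9 at p = 10%, 1.7 at p = 30%) and by less when subjects are correlated with themselves (1.4 at p = 20% and ρ = 0.5, from 28/20). These sizes rest on assumed risks and correlations, equal risk across regimens, subject-level counting and full completion. The distortion is confined to at-least-once percentages. The mixing of formulation with food in the fasted column does not depend on any assumed rate. Separately, the SAP and Protocol 13.1.5 give different groupings for Cohort 17 safety and have to be reconciled in any case.

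**What to change.** In SAP 7.12 and 7.12.1 to 7.12.4, state that Cohort 17 safety is tabulated by Regimen A, Regimen B and Regimen C plus overall, with the subjects dosed in each regimen as that column's denominator and events assigned to the regimen most recently taken. Food is then read as C against B (same tablet) and formulation as B against A (both fasted), matching the contrasts that the PK analysis is meant to estimate. Amend Protocol 13.1.5 to the same layout, or record the departure from it in the SAP.

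The cost is a few lines of wording and one extra table column. No new data are needed, because regimen follows from randomised sequence and period.

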7.12.1 Adverse Events

A PTE will be defined as any untoward medical occurrence in a clinical investigation subject who has signed informed consent to participate in a study but prior to study drug (TAK-071 or placebo) administration or increase in dose/start of donepezil prior to TAK-071 dose. A TEAE will be defined as an AE or a serious AE (SAE) that occurs or gets worse after receiving the first dose of study drug and within 30 days (onset date – last date of dose + 1 ≤ 30) after the last dose of study drug. A TEAE may also be a pretreatment AE or a concurrent medical condition diagnosed prior to the date of first dose of study drug that increases in severity after the start of dosing. AE data with onset occurring more than 30 days after last dose of study drug (AE start date – last dose date > 30) will be listed, but not included in the summary tables.

AE verbatim reported terms will be coded by system organ class, high-level term and preferred term using MedDRA, version to be delineated in the CSR.

TEAE summary tables will include numbers and percentages of subjects experiencing at least one AE by system organ class (SOC) and preferred term (PT) and will be tabulated for SRD

cohorts, non-Japanese MRD cohorts, Japanese MRD cohorts, Cohort 16, and Cohort 17. TEAEs will be summarized according to the treatment most recently received prior to the onset of the event. The TEAE summaries for SRD cohorts, non-Japanese MRD cohorts, Japanese MRD cohorts will also include a treatment group for TAK-071 overall, including all TEAEs summarized for any dose level of TAK-071.

The following is a list of AE summary tables to be generated:

- Overview of TEAEs.
- TEAEs by SOC and PT at subject and event level.
- Subject Mappings for TEAEs.
- TEAEs by PT.
- Most Frequent TEAEs by PT.
- Most Frequent Non-Serious TEAEs by PT.
- Relationship of TEAEs to Study Drug by SOC and PT.
- Drug-Related TEAEs by SOC and PT.
- Intensity of TEAEs by SOC and PT.
- Intensity of Drug-Related TEAEs by SOC and PT.
- Pretreatment Events by SOC and PT.

A subject with 2 or more different AEs within the same level of the MedDRA term and TAK-071 dose level and pooled placebo will be counted only once in that level using the most extreme incident for the intensity tables, and related events to study drug for the causality tables.

Most frequent TEAEs are defined as the AEs occurring in at least 2 subjects in any treatment (ie, pooled placebo or individual dose level).

Data listings will be provided for all AEs (including pretreatment events for enrolled subjects), AEs leading to study drug discontinuation, SAEs, and AEs resulting in death.

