4.2 Rationale for the Proposed Study

A broad program of nonclinical studies has already been performed to explore the pharmacology, PK, and toxicological potential of TAK-071 in animals and in vitro. Those studies indicate that TAK-071 is a selective and specific M₁R PAM, with good oral bioavailability and PK properties

as well as a toxicological profile that is not anticipated to present an unacceptable risk to humans at the proposed clinical doses.

The activation of M₁R is expected to achieve significant cognitive improvement without cholinomimetic-related side effects, including diarrhea, which is seen with donepezil and other cholinesterase inhibitors, and thus has the potential to be a treatment with an improved side effect profile for dementia with Lewy bodies and AD.

This is the first study involving dosing of TAK-071 to humans. Therefore, the main aim of this multipart single-rising dose (SRD) and multiple-rising dose (MRD) study is to explore the safety and tolerability of single and multiple doses of TAK-071 in healthy (non-Japanese) subjects. After confirmation of the acceptable safety and tolerability of TAK-071 alone, a subsequent aim of this study is to explore the safety and tolerability in combination with donepezil in healthy subjects (non-Japanese) because this is the gold standard treatment for AD, one of the key target populations of later phase TAK-071 clinical studies.

Healthy Japanese subjects will be included to investigate any ethnic differences in the safety, tolerability, and/or PK of TAK-071. This part of the study is anticipated to enable Japanese subjects to be recruited into global phase 2 and 3 clinical studies.

Following confirmation of the acceptable safety and tolerability of TAK-071 both alone and in combination with donepezil in healthy subjects, subjects with mild cognitive impairment (MCI) or mild AD (non-Japanese) will also be exposed to combination treatment with the main objective of obtaining early safety and tolerability data in the target population.

This study is intended to explore the safety and tolerability of single and multiple TAK-071 doses, some of which may exceed doses anticipated to be therapeutically effective. However, it should be noted that the study is not intended to determine the maximum tolerated dose (MTD).

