6.1.2.1 Non-Japanese Subjects (Cohorts 7 to 9)

Dose escalation will progress through 3 cohorts. Subjects will be confined during the Treatment Period from Day -1 to Day 22 (Cohorts 7 and 8) or Day 29 (Cohort 9).

For Cohorts 7 and 8, healthy subjects will be randomized to receive multiple doses (21 oral doses QD) of TAK-071 or matching placebo in a 3:1 ratio.

For Cohort 9, TAK-071 or placebo will be administered as a single oral dose, followed by a 7-day washout period and then daily dosing for 21 days or matching placebo in a 3:1 ratio. The 7-day

washout period in Cohort 9 is intended to provide sufficient time to characterize the TAK-071 terminal disposition phase, but it is not expected to result in complete disappearance of TAK-071 from plasma prior to starting repeat dosing on Day 8. Nonetheless, Day 8 trough concentrations are expected to be very low (ie, <5% steady state C_{max}).

For Cohort 9, the potential for time dependency in PK will be evaluated. CSF samples will also be obtained at 5 selected time points after the dose on Day 28 via an indwelling cannula to provide an indication of brain penetration and the concentration relative to circulating plasma concentrations at steady-state of TAK-071. ^{CCI}

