8.1.3 Dose and Regimen

The investigator or investigator's designee will instruct the subject on dosing procedures. All dosing will occur while subjects are in the clinic under the supervision of the principal investigator

or designee (except Days -18 to -11 during Cohorts 10 to 12 where the subject will self-administer donepezil and Days 3 to 10, 12 to 19, 43 to 50, and 52 to 59 during Cohort 16 where the subject will self-administer TAK-071 or placebo each morning at home). The doses taken in the clinic will be administered to the subjects by the investigator or investigator's designee. The exact time of dose will be recorded in the source documents and on the appropriate eCRF.

The planned initial dose of TAK-071 or matching placebo for Cohort 1 is 1 mg. TAK-071 is dosed on the morning of Day 1 after fasting for at least 8 hours. Cohorts 2 through 6, 18, and 19 will escalate through the SRD levels and Cohorts 7 through 9 through the MRD dose levels. Additionally, Cohorts 10 to 12 will be pretreated for 3 weeks with 5 mg donepezil orally continuing through Day 21. In healthy subjects in Cohorts 10 to 12, donepezil will be administered in the morning, shortly before or after TAK-071; the precise relative timing will be confirmed once TAK-071 PK data are available. Cohorts 9 and 13 through 15 will have 1 dose of TAK-071 on Day 1 followed by a 7-day washout period before administration of 21 daily doses of TAK-071. Subjects in Cohorts 20 to 22 will be administered as a single dose of TAK-071 or placebo on Day 1, and a single dose of donepezil or placebo approximately 24 hours later on Day 2.

In Cohort 16, subjects with MCI or mild AD who are stable on donepezil will be randomized to 1 of 2 possible treatment sequences consisting of 2 periods and 2 treatments, alternating in a crossover fashion. In each period, subjects will receive 1 of the following treatments: TAK-071 QD for 21 days (Treatment A) or 21 days of matching placebo (Treatment B). Background 10 mg QD donepezil treatment will be administered in the evening just before bedtime.

In Cohort 17 (Relative BA and FE), TAK-071 DIC or tablet will be administered as a single dose (Regimen A, B, and C) in a cross-over design over 3 periods, with a 21-day washout after each treatment. The planned dose is 10 mg in each of the 3 periods. Diet assigned to each regimen is described in Section 7.4.

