10.2 Procedures

10.2.1 Collection and Reporting of AEs

10.2.1.1 PTE and AE Collection Period

Collection of PTEs will commence from the time the subject signs the informed consent to participate in the study and continue until the subject is first administered study drug (TAK-071) (Day 1 for Cohorts 1 to 9, 13 to 15, and 17 to 22; Day -21 for Cohorts 10 to 12; and Day 1 [if on stable 10 mg dose at Screening] or Day -21 [if donepezil dose increased to 10 mg in subjects already on donepezil 5 mg], or Day -49 [if donepezil initiated as 5 mg dose]) or until screen failure. For subjects who discontinue prior to study drug administration, PTEs are collected until the subject discontinues study participation.

Collection of AEs will commence from the time that the subject is first administered study drug (Day 1 for Cohorts 1 to 9, 13 to 15, and 17 to 22; Day -21 for Cohorts 10 to 12; and Day 1, Day -21, or Day -49 as the case may be [see above]). Routine collection of AEs will continue until the Follow-up Telephone Call/Visit (Day 12 for Cohorts 1 to 6 and 18 to 21, Day 32 for Cohorts 7 to 8 and 10 to 12, Day 39 for Cohorts 9 and 13 to 15, Day 72 for Cohort 16, and Day 28 for Cohort 17).

For subjects in Cohort 16 who receive donepezil during the run-in period, they will be followed-up for PTEs/AEs via weekly phone calls during the run-in period.

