4.0 OBJECTIVES

4.1 Primary Objective

The primary objectives of this study are as follows:

- To characterize the safety, tolerability, and plasma pharmacokinetic (PK) profile of TAK-071 when administered as single and multiple once daily (QD) oral doses at escalating dose levels in healthy subjects (non-Japanese).
- To characterize the safety, tolerability, and plasma PK profile of TAK-071 when administered as single and multiple QD oral doses at escalating dose levels in healthy subjects (non-Japanese) in the presence of steady-state exposure of donepezil QD.
- To characterize the safety, tolerability, and plasma PK profile of TAK-071 when administered as single and multiple QD oral doses at escalating dose levels in healthy Japanese subjects.
- To characterize safety, tolerability, and plasma PK profile of 10 mg donepezil when administered as a single dose, and to compare it to combination of 10 mg donepezil+TAK-071.
- To characterize the safety, tolerability, and plasma PK profile of TAK-071 when administered as multiple QD oral doses to subjects with mild cognitive impairment (MCI) or mild Alzheimer Disease (AD) (non-Japanese) receiving donepezil treatment for a minimum of 3 months.

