5.0 ANALYSIS ENDPOINTS

5.1 Primary Endpoints

The following safety parameters will be analyzed as primary endpoints:

- Percentage of subjects who have at least 1 treatment-emergent adverse event (TEAE).
- Percentage of subjects who meet the Takeda markedly abnormal value (MAV) criteria at least once postdose for the following:
 - Clinical laboratory parameters.
 - Vital sign measurements.
 - ECG parameters.

PK parameters of TAK-071 in plasma following a single dose (Day 1) and at steady-state (after the final dose following multiple dosing) will be analyzed as primary endpoints:

- t_{\max} .
- C_{\max} in plasma.
- Area under the plasma concentration-time curve from time 0 to 24 hours (AUC_{24}).
- Area under the plasma concentration-time curve from time 0 to infinity, calculated using the observed value of the last quantifiable concentration (AUC_{∞}) (single dose only [Day 1]).

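### Cohorts 9 and 13 to 15: the single-dose week is merged into the multiple-dose TEAE and MAV percentages, so Japanese single-dose safety has no table and comparisons with Cohorts 7 and 8 tend to be uneven

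*SAP*

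**What the plan says.** - **Regimen.** Protocol 8.1.3: "Cohorts 9 and 13 through 15 will have 1 dose of TAK-071 on Day 1 followed by a 7-day washout period before administration". The daily phase that comes next has 21 doses. Under Protocol 6.1.2.1, Cohorts 7 and 8 receive 21 daily doses from Day 1 with no lead-in dose.
- **AE collection.** Protocol 10.2.1.1 ends routine collection on "Day 32 for Cohorts 7 to 8 and 10 to 12, Day 39 for Cohorts 9 and 13 to 15". In all four of these non-donepezil groups it starts at the Day 1 dose.
- **TEAE rule.** SAP 7.12.1 counts an event "that occurs or gets worse after receiving the first dose of study drug", and adds: "TEAEs will be summarized according to the treatment most recently received prior to the onset of the event". Tables are by dose level within the non-Japanese MRD part (Cohorts 7 to 12 in SAP 7.1.3) and the Japanese MRD part.
- **MAV rule.** SAP 5.1: "Percentage of subjects who meet the Takeda markedly abnormal value (MAV) criteria at least once postdose". SAP 7.12.2 to 7.12.4 include scheduled and unscheduled postdose results.
- **Exposure.** SAP 7.8 plans no summary of extent of exposure, so nothing adjusts for time observed.
- **Objective.** SAP 4.1 seeks to characterize safety, tolerability and PK of TAK-071 "administered as single and multiple QD oral doses at escalating dose levels in healthy Japanese subjects". Protocol 4.2: "Healthy Japanese subjects will be included to investigate any ethnic differences in the safety, tolerability, and/or PK of TAK-071".
- **Dose matching.** Protocol 6.2.2.2 gives Cohorts 13, 14 and 15 the doses of Cohorts 7, 8 and 9.

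**The concern.** A subject-level percentage of the at-least-once kind depends on how long and how often each subject is observed. Cohorts 9 and 13 to 15 have one more dose, one more week and more assessments than Cohorts 7 and 8, and the SAP tables do not separate that week.

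The first consequence is a gap. SAP 7.12 speaks of Japanese SRD cohorts, but Cohorts 13 to 15 are the only Japanese cohorts and all belong to the MRD part. Their Days 1 to 7 are the only single-dose safety data in Japanese subjects. Merging them with daily dosing leaves the single-dose half of a primary objective without a TEAE or MAV result.

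The second is a tilt in two comparisons that readers will make: Cohort 9 against Cohorts 7 and 8 in the non-Japanese table, and Cohorts 13 and 14 against their dose matches, Cohorts 7 and 8, when the two tables are laid side by side.

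**Working it through.** **1. The plan's own figure on observation length.** The Study Summary (Protocol 2.0) gives a period of evaluation for each cohort. Screening days plus follow-up day reproduces it for Cohorts 7 and 8 (28 + 32 = 60), the SRD cohorts (28 + 12 = 40) and Cohorts 10 to 12 (44 + 32 = 76). For Cohorts 9 and 13 to 15 it gives 28 + 39 = 67, where the summary states about 57. The stated figure suggests a shorter observation than in Cohorts 7 and 8; the follow-up day shows a longer one. The passages should be reconciled, but nothing below uses the 57.

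**2. Opportunities to be counted** (nominal days; schedules from Protocol 10.2.1.1 and SAP 7.12.2 and 7.12.4).

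| | Cohorts 7, 8 | Cohorts 9, 13 to 15 | Ratio |
|---|---|---|---|
| Doses | 21 | 1 + 21 = 22 | 1.05 |
| AE window (days) | 32 | 39 | 1.22 |
| Postdose ECGs | 5 + 20 + 2 = 27 | 5 + 6 + (1 + 5) + 22 = 39 | 1.44 |
| Laboratory days | 9 | 12 | 1.33 |

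The ECG terms for Cohorts 7 and 8 are Day 1, Days 2 to 21, and Days 22 and 23. For the other cohorts they are Day 1, Days 2 to 7, Day 8 (predose plus five), and Days 9 to 30. The 30-day limit in the TEAE definition does not bind, because routine collection stops earlier.

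**3. Expected shift with no true difference.** The documents give no event rates, so the base rate p in Cohorts 7 and 8 is assumed. With constant risk per day or per assessment, p' = 1 − (1 − p)^ratio.

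| p | TEAE (39/32) | Laboratory MAV (12/9) | ECG MAV (39/27) |
|---|---|---|---|
| 20% | 23.8% (+3.8) | 25.7% (+5.7) | 27.6% (+7.6) |
| 50% | 57.0% (+7.0) | 60.3% (+10.3) | 63.3% (+13.3) |
| 70% | 76.9% (+6.9) | 79.9% (+9.9) | 82.4% (+12.4) |

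The largest TEAE shift is 7.3 points: 0.073 × 6 = 0.44 of a subject in a cohort with 6 active subjects, and 0.073 × 5 = 0.36 with 5. One subject is 16.7 or 20 points. At p = 50% and 6 per cohort, the chance that Cohort 9 shows strictly more subjects with a TEAE than Cohort 8 is 48.5%, against 38.7% with equal windows.

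**4. Sensitivity.** Repeated laboratory and ECG values in one subject are correlated, so those two columns lie towards the upper end. In the other direction, if all TEAE risk sat at each start of dosing and both starts carried it equally, 30% would become 1 − 0.7² = 51%. That is an extreme case, not an estimate.

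**5. Where the tilt is absent or reverses.** All Japanese cohorts, including their placebo subjects, share one schedule. Cohort 15 and Cohort 9 have the same AE window. For vital signs, Protocol 9.1.6 gives Cohort 9 supine measurements only, while three of the seven rows in SAP Appendix B are orthostatic. Scheduled orthostatic sets are 5 + 22 = 27 in Cohorts 7 and 8, 0 in Cohort 9, and 5 + 29 = 34 in Cohorts 13 to 15.

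**6. Effect of splitting at the Day 8 dose.** The multiple-dose phase then has an AE window of 32 days against 32, ECGs 27 against 27, and laboratory days 8 against 9 (the Day 8 sample is predose).

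**The case against.** **The comparisons are not planned tests.** The Japanese comparison that Protocol 6.1.2.3 and 13.1.3 describe is one of PK, dose matching is justified by exposure, and laboratory and vital-sign summaries carry no tests. This stands. It limits point (b) to descriptive reading, although Protocol 4.2 names ethnic differences in safety as a purpose.

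**The single-dose data are not lost.** Laboratory and vital-sign results are summarized at each time point, and AEs are listed with dates and times. This also stands: only the subject-level TEAE and MAV percentages are merged. Those percentages are the primary safety endpoints, however, and the gap in (a) depends on no assumed rate.

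**A reader might infer that Japanese subjects and the top dose must look less safe by construction.** The documents do not support that. The expected TEAE shift is under half a subject, the Japanese table is internally balanced, and Cohort 9 cannot meet the orthostatic criteria at all.

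**A reader might also infer a clean confounding of window length with dose in the non-Japanese table.** That part also contains Cohorts 10 to 12, and the Protocol counts donepezil as study drug. If their run-in is counted (21 + 32 = 53 days), mean pooled-placebo time is (4 × 32 + 2 × 39 + 6 × 53)/12 = 43.7 days, longer than the 39 of Cohort 9. Without the run-in it is (10 × 32 + 2 × 39)/12 = 33.2 days.

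**Counting only from Day 8 would bias the other way.** First-exposure events would drop out of Cohorts 13 and 14 but stay in Cohorts 7 and 8. Restricting MAVs to matched days would leave 6 of the 9 laboratory days in Cohorts 7 and 8 (Days 2, 8, 20, 21, 22 and 23) and discard unscheduled values. This is right, and it is why the phase columns should supplement the whole-period tables rather than replace them.

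**Conclusion.** The point holds in two limited parts.

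(a) Japanese single-dose safety, named in the third primary objective, has no TEAE or MAV table. This follows from the cohort structure and the table definitions alone.

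(b) TEAE, laboratory MAV and ECG MAV percentages tend to be somewhat higher in Cohort 9 than in Cohorts 7 and 8, and in Cohorts 13 and 14 than in their dose matches. For TEAEs the tendency is about 4 to 7 points, assuming a constant hazard and a base rate of 20% to 70%. It is a tendency, not a certain result, and it reverses for orthostatic MAVs at Cohort 9.

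Both parts assume that the lead-in dose equals the daily dose within a cohort, so that the most-recent-treatment rule does not separate the phases. The documents imply this but do not say so outright.

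**What to change.** Keep the whole-period tables. In SAP 7.12, for Cohorts 9 and 13 to 15, active and placebo alike, add TEAE and MAV columns by phase:

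- **Single dose:** Day 1 dose to predose Day 8.
- **Multiple dose:** Day 8 dose to follow-up.

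Keep the pre-Day 1 baseline for both phases and include all unscheduled values. Report the single-dose columns of Cohorts 13 to 15 as the Japanese single-dose safety result. When Cohort 9, 13 or 14 is read against Cohorts 7 and 8, show the multiple-dose columns beside the whole-period columns.

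Add a footnote that subjects entering the multiple-dose phase have already had one dose, so first-exposure events fall in the single-dose phase. Report orthostatic MAVs only for cohorts that measured them.

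The cost is SAP wording and extra table columns; no new data are needed. The drawback is small counts per phase, with 5 or 6 active subjects per cohort.
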